## 5.2. Analyses for Dose Escalation Cohorts and Expansion Phases

In the dose escalation cohorts, the dose will be escalated based on all available data, including biomarker, PK data, and the safety profile of prior cohorts. In addition, the recommended dose from a Continuous Reassessment Method (N-CRM) analysis [[Neuenschwander, 2008](#)] will be calculated. The N-CRM is a type of Bayesian adaptive dose-escalation scheme. The method is fully adaptive and makes use of all the DLT information available at the time of each dose assignment. The Fixed and Adaptive Clinical Trial Simulator (FACTS) will be used to conduct the N-CRM analysis. The DLT information on all subjects enrolled in the trial are used to update the estimated dose-toxicity relationship and provide supportive information in addition to the 3+3 design in the next escalation/de-escalation decision.

There is no futility analysis for dose expansion cohorts as specified in [Section 5.1](#).

## 5.3. Final Analyses

The final analysis of the study will be performed when the study is completed or terminated. Upon Protocol Amendment 4 implementation, ongoing subjects will be considered withdrawn due to study closure and will be followed for up to 3 months after the last dose. Only when a subject dies is he/she considered to have completed the study; consequently, “death” is not listed as a reason for withdrawal from the study. Furthermore, disease progression, discontinuation of study treatment, and AEs, are not by themselves reasons for withdrawal from the study. If a subject dies a copy of the death certificate should be available for review, if possible, and the cause of death should be evaluated and documented.

The end of the study is defined as the last subject’s last visit.

# 6. SAMPLE SIZE CONSIDERATIONS

## 6.1. Sample Size Assumptions

The sample size for each part of the trial was chosen to adequately characterize the safety, clinical activity, PK, and pharmacodynamic marker data according to the objectives of each part of the study.

The study will enroll up to approximately 264 subjects with tumor types that may include NSCLC, SCCHN, RCC, melanoma, STS, bladder cancer, TNBC, and MSI CRC.

Up to 72 subjects will be enrolled in each of the two dose escalation parts of the study (Parts 1A and 2A); up to 30 subjects will be enrolled in each of dose expansion cohorts. The sample size of each expansion cohort at a given dose level will be minimum of 10 subjects and maximum of 30 subjects based on the overall response assessments. More details of sample size calculation are described in protocol Section 9.2.

## 7. ANALYSIS POPULATIONS

### 7.1. All Treated Population

The **All Treated Population** is defined as all subjects who receive at least one dose of GSK3174998. Safety and anticancer activity will be evaluated based on this analysis population.

### 7.2. PK Population

The **PK Population** will consist of all subjects from the All Treated Population for whom a PK sample is obtained and analyzed.

### 7.3. Analysis Datasets

Analysis datasets will be created according to CDISC/ADaM standards, and data will be listed and summarized according to GSK Integrated Data Standards Library (IDSL) reporting standards. Formatting for dates, times, and decimal places will follow GSK standards except where specified.

## 8. TREATMENT COMPARISONS

There are no treatment comparisons in the study.

### 8.1. Data Display Treatment and Other Subgroup Descriptors

For Part 1 (i.e., Part 1A), Monotherapy: Investigated doses of GSK3174998 will be displayed in summary tables and listings.

For Part 2A, Combination Dose Escalation: Some AE and exposure tables and listings will be displayed for GSK3174998 and pembrolizumab separately, all other tables and listings will display by dose levels of both GSK3174998 plus pembrolizumab.

For Part 2B, Combination Dose Expansion: Data will be displayed by each cohort type at the recommended phase 2 dose; for combination therapy expansions, selected AE and exposure display requirements as noted in Part 2A will also apply.

## 9. GENERAL CONSIDERATIONS FOR DATA ANALYSES

SAS 9.3 or higher version will be used to perform all data analyses, generate tables, figures, and listings. The exception would be CRM analyses, which are specified to take place in FACTS.

All data within scheduled visits up to the time of study completion/withdrawal from study will be included in the analysis summaries, regardless of duration of treatment. Unscheduled visits will be considered for most extreme result reporting (e.g. worst grade post-baseline) and included in data listings.

Actual treatment derivation is specified in [Section 10.2.10](#). Planned treatment is collected on dosing regimen eCRF page.

Efficacy analysis will be based on planned treatment.

For Part 1 and Part 2A, Safety and PK analysis will be based on actual treatment the subjects received and displayed by dose level. Efficacy analysis will be based on planned treatment and displayed by dose level.

For Part 2B, tables and figures will be displayed by cohort type. The subject will be summarized in the cohort type though the actual dose level may be different from the planned dose level. A footnote will be added in the Safety and PK table or figure to explain the discrepancy.

Unless otherwise noted, Safety and PK listings will be based on the actual treatment and efficacy listings will be based on the planned treatment.

In addition, for PK and receptor occupancy analysis, if a subject received different doses of treatment, the subject will be excluded from the analysis.

Deviations from the analyses in the RAP will be identified in the CSR.

Unless otherwise noted, the denominator for the percentage is the number of subjects in the analysis population used for the summary.

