If a subject experiences a DLT in the first 4 weeks of treatment, the subject will be discontinued from study therapy unless the investigator considers it in the best interest of the subject to continue on study (e.g., in case of tumor regression, symptomatic disease improvement, and/or if the type of DLT is viewed as preventable in subsequent cycles, e.g., by pre-medication). Such cases will require approval by the Sponsor before continuation on study treatment at the same or lower dose.

Guidance for the management of toxicity, including dose modification algorithms, is provided in Section 6.3.1 and is based on the experience of management of immune-related adverse events (irAEs) since the development of ipilimumab and PD-1 inhibitors such as pembrolizumab.

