4.1.6. Intra-Subject Dose Escalation

There will be no intra-subject dose escalation.

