9.4.2.2.2. Statistical Analysis of Pharmacokinetic Data

Statistical analyses of the PK parameters data will be the responsibility of Clinical Statistics, GSK.

Drug concentration-time data will be listed for each subject and summarized by descriptive statistics at each time point by cohort. PK parameter data will be listed for each subject and summarized by descriptive statistics by cohort.

The data from this study may be combined with the data from other studies for a population PK analysis, which will be reported separately.

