### **10.2.10. Actual Treatment**

The actual treatment of a subject will be derived from exposure data. The first dose the subject received is used as actual treatment.

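### A subject given different doses is removed whole from the PK and receptor-occupancy analysis, so a valid first-dose profile can leave small dose-level summaries

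*SAP*

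**What the plan says.** SAP section 9 (General Considerations for Data Analyses) states for PK and receptor occupancy that "if a subject received different doses of treatment, the subject will be excluded from the analysis". It does not define a different dose and sets no tolerance. It has no cut-off at the time of the change and no sensitivity analysis.

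Other parts of the plan treat the same subjects differently:

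- SAP 7.2 defines the PK Population as "all subjects from the All Treated Population for whom a PK sample is obtained and analyzed".
- Protocol 9.4.2.2.2 says that "PK parameter data will be listed for each subject and summarized by descriptive statistics by cohort", with no exclusion for a dose change.
- SAP 10.2.10 settles the dose label: "The first dose the subject received is used as actual treatment".
- For Part 2B, SAP section 9 itself keeps the subject: "The subject will be summarized in the cohort type though the actual dose level may be different from the planned dose level". It then adds: "A footnote will be added in the Safety and PK table or figure to explain the discrepancy".

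On how doses may change within a subject, Protocol 4.1.6 says "There will be no intra-subject dose escalation". For subjects who continue after a dose-limiting toxicity (DLT), Protocol 4.1.4 says "Such cases will require approval by the Sponsor before continuation on study treatment at the same or lower dose". The synopsis ties dose adjustments to tolerability and safety.

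**The concern.** Samples taken before a dose change belong to the dose that was given. A later change is no reason to drop them, yet the rule as written drops the whole subject. The PK parameters concerned (Cmax, AUC(0-τ), Cmin) are secondary endpoints in both parts. Receptor occupancy is exploratory. Both are described by dose level, where a level may start with up to 4 subjects and is capped at 12 (Protocol 4.1.1), so a single subject carries weight.

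The second worry is which subjects go. Upward changes within a subject are barred and adjustments are linked to tolerability, so a change of dose may go with poor tolerance, and perhaps with exposure. Dose-level exposure would then be summarised in a subset chosen partly by outcome.

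**Working it through.** **1. Is the first-dose profile complete before a change can occur?** Protocol Table 14, dose escalation:

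| Measure | First-dose samples | Second-dose samples |
|---|---|---|
| GSK3174998 PK | Days 1, 2, 8, 15, and Day 22 pre-dose | Day 22 after infusion, Days 23, 29, 36, and Day 43 pre-dose |
| Receptor occupancy | Days 1, 2, 8, 15, and Day 22 pre-dose | Day 22 after infusion, and Day 43 pre-dose |

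Dose 2 is given on Day 22. A change at dose 2 leaves the first-dose column untouched. A change at dose 3 or later leaves both columns untouched. The rule removes all of it in either case. If the change is at dose 2, the second column belongs to the new dose, so only the first-dose profile is safe in every case.

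**2. Is there a dose label for these data?** Yes. SAP 10.2.10 assigns the first dose received, so the retained samples need no new convention.

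**3. How many subjects?** The documents give no count. What can be bounded, from Protocol 2.3.5 and 4.5.3 at the 13 August 2019 cut-off:

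- Subjects: 45 monotherapy + 96 combination − 3 who crossed over = 138, which matches the stated total.
- DLTs: none on monotherapy and two in combination. Continuation at a lower dose after a DLT therefore covers at most 2 of 138 (1.4%).
- Protocol Tables 10 and 12 contain no dose-reduction step. Reductions are still anticipated: they are part of the primary endpoint, and SAP 13.2 tabulates AEs leading to them.

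**4. What does one exclusion cost?** SAP 15.2 reports 95% confidence intervals for the arithmetic and geometric means by dose level. At equal SD:

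- standard error factor = √(n/(n−1))
- interval factor = [t(0.975, n−2)/√(n−1)] ÷ [t(0.975, n−1)/√n]

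| n to n−1 | Share lost | SE factor | 95% CI factor |
|---|---|---|---|
| 4 to 3 | 25% | √(4/3) = 1.155 | (4.303/√3) ÷ (3.182/√4) = 1.56 |
| 6 to 5 | 17% | √(6/5) = 1.095 | (2.776/√5) ÷ (2.571/√6) = 1.18 |
| 12 to 11 | 8% | √(12/11) = 1.044 | (2.228/√11) ÷ (2.201/√12) = 1.06 |

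A level of 4 is not hypothetical: Protocol 4.5.3 reports 4 subjects at 10 mg/kg plus pembrolizumab. No document says that any of them changed dose.

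**5. Could the mean shift?** Only under assumptions. Suppose exposure is log-normal with a CV of 20% to 50% (assumed) and the one subject removed has the highest exposure (assumed). Simulation (200,000 draws) then gives a geometric mean lower by about 7% to 15% at n = 4 and 3% to 7% at n = 12. Removing the lowest shifts it upward by the reciprocal factor. If removal is unrelated to exposure, the expected shift is zero.

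**The case against.** The strongest reply is that this is a narrow data-handling rule that may touch almost nobody. It is descriptive throughout: SAP 15.3 plans no statistical analysis of PK data. Under Protocol 4.1.4 a subject with a DLT stops treatment by default, and an approved continuation may be at the same dose. That stands, and it limits the size of the point. It does not supply a reason to drop a first-dose profile.

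Several stronger readings are tempting, and the documents do not support them:

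- **The rule contradicts the PK Population.** A population definition sets membership, and an analysis may exclude further within it. Protocol 9.4 also allows additions to be documented in the analysis plan. The rule is stricter than the population, not inconsistent with it.
- **The Part 2B rule is flatly contradicted.** That holds only if different doses means different from plan. If it means varying between infusions, the triggers differ. The text does not say which.
- **The data vanish from the report.** Protocol 9.4.2.2.2 and SAP 15.1 and 15.2 list concentrations and derived parameters. Section 9 does not say that listings are affected. The loss shown is to summaries.
- **Crossover subjects are removed.** SAP 11.3 treats them as re-enrolled, and SAP 8.1 sets out Parts 1 and 2A separately. Nothing says that doses are pooled across parts.
- **The 0.3 mg/kg choice was affected.** Amendment 3 already made that choice. This SAP cites Amendment 4, so the rule came later.

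**Conclusion.** The concern holds in a limited form. As written, the rule takes valid first-dose data out of the dose-level PK and receptor-occupancy summaries without an analytic reason. It is stricter than the PK Population and than the keep-and-footnote treatment of Part 2B in the same section.

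Per excluded subject, the 95% interval widens by a factor of about 1.56 at a level of 4 and about 1.06 at a level of 12, assuming equal SD. How often this happens is not stated and may be rare. A reader might infer that the rule selectively removes subjects who had a DLT. The documents support only that removal may be related to tolerability; they establish neither the size nor the direction of any bias. Receptor occupancy is affected in Parts 1A and 2A only, and no formal test depends on the result.

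The conclusion rests on reading the sentence as a subject-level exclusion without a time limit, which is its natural meaning.

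**What to change.** Replace the sentence in SAP section 9 with:

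> For PK and receptor occupancy, samples taken before the first administered dose of GSK3174998 that differs from the first dose received (beyond a stated tolerance for rounding or partial infusion) are included under that first dose; later samples are listed and excluded from dose-level summaries. Part 1 and Part 2 participation of re-enrolled subjects is handled separately. Excluded samples are listed with reasons.

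The team must set the tolerance. The last sentence is needed because the listing in SAP 11.1 covers exclusions from analysis populations, and these subjects remain in the PK Population.

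The cost is a short text replacement and an exclusion flag at record level instead of subject level. The downside is that n varies by time point, so each summary should show its n. This is a cheap improvement and needs no new data.

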### **9.1. Other Strata and Covariates**

In all efficacy analyses, there are no formal plans for any stratification. There are no formal plans for investigating any covariates.

### **9.2. Examination of Subgroups**

There are no formal plans for examining subgroups.

### **9.3. Multiple Comparisons and Multiplicity**

There is no adjustment for multiplicity in all primary and secondary analyses.

## **10. DATA HANDLING CONVENTIONS**

### **10.1. Premature Withdrawal and Missing Data**

For endpoints which determine the percentage of responders, subjects with unknown/not evaluable or missing best overall response will be assumed to be non-responders, and will be included in the denominator when calculating the percentages.

In the event that the study is terminated, all available data will be listed and a review carried out by the study team to assess which statistical analyses are still considered appropriate.

Missing data occurs when any requested data is not provided, leading to blank fields on the collection instrument. These data will be indicated by the use of a “blank” in subject listing displays. Answers such as “Not applicable” and “Not evaluable” are not considered to be missing data and should be displayed as such.

Subjects with the designation of treatment relationship for AEs and SAEs missing will have the worst case assumed to impute the relationship: if relationship to study treatment is missing it will be assumed to be “Yes”. There will be no other imputation for missing data other than what is described in [Section 10.2](#) for partial dates.

## **10.2. Derived and Transformed Data**

The following sections provide a general description of the derived and transformed variables used to describe and analyze the data. Separate analysis dataset specifications provide full details on all data derivations and transformations including descriptions of core standard algorithms and standard oncology algorithms. The analysis dataset specifications will clearly communicate the content and source of the datasets supporting the statistical analyses.

### **10.2.1. Reference dates**

Unless otherwise stated, the safety reference (start) date will be the start of treatment of GSK3174998. This will also be the efficacy reference date for this study. The reference date for baseline characteristics (e.g. age) will be the date of screening.

### **10.2.2. Study Day for Safety Measures**

If the date of interest occurs on or after the safety reference date then the safety study day will be calculated as (date of interest - safety reference date) + 1. There is no safety study day 0.

### **10.2.3. Study Day for Efficacy**

If the date of interest occurs on or after the efficacy reference date then efficacy study day will be calculated as (date of interest - efficacy reference date) + 1. If the date of interest occurs prior to the efficacy reference date then efficacy study day will be calculated as (date of interest – efficacy reference date). There is no efficacy study day 0.

### **10.2.4. Duration and Elapsed Time**

Durations (e.g., the duration of an AE, duration of exposure, etc.) are calculated as the stop date minus the start date plus one.

For elapsed time (e.g., the time since initial diagnosis):

- If the reference date is on or after the event date, then the elapsed time is the reference date minus the event date + 1.
- If the reference date is before the event date then the elapsed time is the reference date minus the event date.

When reporting time to event (TTE) durations in months, divide the number of days by 30.4375; to report in weeks divide the number of days by 7; to report in years divide the number of days by 365.25. These algorithms for time to event return decimal numbers, and ignore the actual numbers of days in the months or years between start date and stop date. The "year" used in these algorithms is 365.25 days long, and the "month" is one twelfth of that year.

For converting all other durations (e.g., duration of AEs, duration of exposure, age) to weeks, months or years use the following:

- To report the duration in weeks, divide the number of days by 7.

- To report the duration in months use:

$$(\text{YEAR}(\text{stopdate} + 1) - \text{YEAR}(\text{startdate})) * 12 + (\text{MONTH}(\text{stopdate} + 1) - \text{MONTH}(\text{startdate}) - 1) + (\text{DAY}(\text{stopdate} + 1) >= \text{DAY}(\text{startdate}))$$

- To report the duration in years use:

$$\text{INTCK}('year', \text{startdate}, \text{stopdate} + 1) - (\text{MONTH}(\text{stopdate} + 1) < \text{MONTH}(\text{startdate}) \text{ or } (\text{MONTH}(\text{stopdate} + 1) = \text{MONTH}(\text{startdate}) \text{ and } \text{DAY}(\text{stopdate} + 1) < \text{DAY}(\text{startdate})))$$

The algorithms above for age and duration return whole numbers for months and years, accurately accounting for the actual numbers of days in the months or years between the start date and the stop date.

### 10.2.5. Imputation of Partial Dates

Imputed partial dates will not be used to derive study day, duration (e.g., duration of AEs), or elapsed time variables.

Imputed dates will not be displayed in listings. However, where necessary, display macros may impute dates as temporary variables for the purpose of sorting data in listings only. In addition, partial dates may be imputed for determining treatment-emergent AEs.

The partial date imputation will follow ADaM conventions. The ADaM approach is to populate the numeric date variables with the imputed date and add a flag variable to the dataset that indicates the level of imputation.

The flag variable can contain the values: blank, 'D', 'M', 'Y'.

blank: indicates that no imputation was done

D='Day': indicates that the day portion of the date is imputed

M='Month': indicates that the month and day portions of the date are imputed

Y='Year': indicates that the entire date (year, month, and day) is imputed

Example of Date Variables:

XYZD\_ - character date variable

XYZDT - numeric date variable

XYZDTFL - flag variable

Details on imputing partial dates for specific datasets are outlined below.

### Adverse Events (AE):

Imputations in the adverse events dataset are used for determining treatment-emergent AEs and for sorting in data listings.

Dataset	Date	Missing Element	Rule
Adverse Events (AE)	Start Date	day, month, and year	
 
• No Imputation for completely missing dates
 

		day, month	
 
• If study treatment start date is missing (i.e. subject did not start study treatment), then set start date = January 1.
 
• Else if study treatment start date is not missing: 
 
○ If year of start date = year of study treatment start date then 
 
- If stop date contains a full date and stop date is earlier than study treatment start date then set start date = January 1.
 
- Else set start date = study treatment start date.
 
 
 
○ Else set start date = January 1.
 
 
 

		day	
 
• If study treatment start date is missing (i.e. subject did not start study treatment), then set start date = 1st of month.
 
• Else if study treatment start date is not missing: 
 
○ If month and year of start date = month and year of study treatment start date then 
 
- If stop date contains a full date and stop date is earlier than study treatment start date then set start date= 1st of month.
 
- Else set start date = study treatment start date.
 
 
 
○ Else set start date = 1st of month.
 
 
 

	End Date		
 
• No imputation for partial end dates will be performed
 

**Surgery:**

Imputed dates will not be displayed in listings. However, where necessary, display macros may impute dates as temporary variables for the purpose of sorting data in listings only.

Dataset	Missing Element	Rule
Surgical Procedures	day, month, and year	
 
• No Imputation for completely missing dates
 

	day, month	
 
• If partial date contains a year only set to January 1st.
 

	day	
 
• If partial date contains a month and year set to the 1st of the month
 

**Concomitant Medication and Blood and Blood Supportive Care Products:**

Imputed dates will not be displayed in listings. However, where necessary, display macros may impute dates as temporary variables for the purpose of sorting data in listings only.

Dataset	Date	Missing Element	Rule
Concomitant Medication Blood and Blood Supportive Care Products	Start Date	day, month, and year	No Imputation for completely missing dates
		day, month	
 
• If study treatment start date is missing (i.e. subject did not start study treatment), then set start date = January 1.
 
• Else if study treatment start date is not missing:           
 
◦ If year of start date = year of study treatment start date then               
 
- If stop date contains a full date and stop date is earlier than study treatment start date then set start date = January 1.
 
- Else set start date = study treatment start date.
 
 
 
 
 
 
Else set start date = January 1.

		day	
 
• If study treatment start date is missing (i.e. subject did not start study treatment), then set start date = 1st of month.
 

Dataset	Date	Missing Element	Rule
Concomitant Medication Blood and Blood Supportive Care Products	End Date	day, month, and year	
 
No Imputation for completely missing dates
 

		day, month	
 
If partial end date contains year only, set end date = earliest of December 31 or date of last contact.
 

		day	
 
If partial end date contains month and year, set end date = earliest of last day of the month or date of last contact
 

